#### 3.1.4.1 Non-hematologic AEs

- Grade 3 nausea, vomiting, or diarrhea that persist  $\leq$  7 days with supportive care
- Grade 3 fatigue with improvement to  $\leq$  grade 2 within 7 days
- Grade 3 infection that improves to  $\leq$  grade 2 after initiation of antimicrobials
- Grade 3 electrolyte disturbances that improve to  $\leq$  grade 2 within 72 hours with appropriate medical management and are not associated with other clinically significant consequences.
- Grade 3 magrolimab- or obinutuzumab-infusion reactions that resolve to  $\leq$  grade 1 within 24 hours. **NOTE:** In a patient, if it is not clear if the AE is an infusion-related reaction (IRR), the patient may be replaced.
- Other grade 3 laboratory abnormality that is asymptomatic and deemed by the investigator to be not clinically significant

#### 3.1.4.2 Hematologic AEs

- Grade 3 neutropenia not associated with clinical sequelae
- Grade 3 thrombocytopenia not associated with  $\geq$  grade 2 bleeding
- Grade 3 anemia that lasts less than 3 days and responds to blood transfusion. **NOTE:** Grade 3 hemolytic anemia that requires hospitalization or prolongation of existing hospitalization, is disabling, or limits self-care activities of daily life (ADLs) will be considered a DLT.
- Grade 3 or 4 lymphopenia

### 3.1.5 Safety Ramp-Up of Venetoclax

Patients with FL (Arms 1 and 3; Cohorts 1 and 3) will start venetoclax at target dose for that particular dose level.

Intra-patient dose escalation of venetoclax will be performed with fixed doses of magrolimab and obinutuzumab for patients with MZL, MCL and CLL (Arms 2 and 4; Cohorts 2, 4, 5 and 6) during Cycle 1 (**Table 10**). If tolerated, venetoclax will be administered at the target dose level once daily for all subsequent cycles.

**NOTE:** During safety ramp-up, an individual patient who experiences a DLT or toxicity that meets DLT criteria during dose expansion (serious toxicity) can have venetoclax dose reduced to the dose of venetoclax that was tolerated and continue treatment (**Table 10**), if felt to be in the best interests of the patient. Once DLT assessment is complete, all dose modifications during safety ramp-up will be conducted per Sections **3.3.2** and **3.3.3**. DLT rules apply to all arms.

**Table 10: Intrapatient ramped-up dose-escalation schedule for venetoclax in MZL, MCL and CLL patients**

| Week of safety ramp-up period | Patients with MZL, MCL and CLL (Arms 2 and 4) |                |
|-------------------------------|---|----------------|
|                               | DL(-1):
200 mg                             | DL1:
400 mg |
| 1                             | 20 mg   | 20 mg          |
| 2                             | 50 mg   | 50 mg          |
| 3                             | 100 mg  | 100 mg         |
| 4                             | 200 mg  | 200 mg         |
| 5                             | 200 mg  | 400 mg         |

### **3.2 DRUG ADMINISTRATION**

Treatment schedule from Cycles 1 to 12 is provided below ([Table 11](#) and [Table 12](#) for dose-finding and dose-expansion respectively). A flexibility window between cycles of -3/+7 days is allowed due to scheduling or other administrative reasons; additional delays may apply based on toxicities.

Magrolimab doses will be calculated based on actual body weight measured at the most recent clinical assessment prior to administration. Patients will be encouraged to complete and return an optional drug diary as a memory aid to help document the date and time of all self-administered study drugs ([Appendix D](#)). This drug diary as well as study drug containers and any unused study drug should be returned to the research team at the end of each cycle of therapy.

**Table 11: Drug administration schedule for study medications for dose-finding cohorts**

| Arm | Drug a,b,c | Cycle 1
Arm 1: 28 days
Arm 2: 35 days  | Cycles 2-12
Arms 1 and 2: 28 days |
|-----|-----------------------|---|---|
| 1   | Magrolimab     | D2: 1mg/kg
D8,15,22: 30mg/kg   | D1,15: 30mg/kg                       |
|     | Obinutuzumab   | D1: 100mg
D2: 900mg
D8,15: 1000mg  | D1: 1000mg                           |
|     | Venetoclax     | D1-28:
DL1: 800mg
DL(-1): 600mg  | D1-28:
DL1 800mg
DL(-1) 600mg  |
| 2   | Magrolimab     | D2: 1mg/kg
D8,15,22: 30mg/kg   | D1,15: 30mg/kg                       |
|     | Obinutuzumab   | D1: 100mg
D2: 900mg
D8,15: 1000mg  | D1: 1000mg                           |
|     | Venetoclax     | DL1:
D1-7: 20mg
D8-14: 50mg
D15-21: 100mg
D22-28: 200mg
D29-35: 400mg

DL(-1):
D1-7: 20mg
D8-14: 50mg
D15-21: 100mg
D22-28: 200mg
D29-35: 200mg | D1-28:
DL1 400mg
DL (-1) 200mg |

a When both magrolimab and obinutuzumab are given on the same visit day, obinutuzumab will be administered at least 1 hour after the completion of magrolimab administration.

b Premedication with acetaminophen 650 mg and diphenhydramine 25-50mg (or comparable regimen) will be administered 30-60 minutes prior to all obinutuzumab doses. Similar premedication will also be given prior to priming dose and first loading dose of magrolimab. Additional premedication with dexamethasone 4 to 20 mg or comparable regimen will be given before the priming dose and first loading dose of magrolimab. Premedication is not required for subsequent doses of magrolimab.

c Obinutuzumab and magrolimab are administered as intravenous infusions.

**Table 12: Drug administration schedule for study medications for expansion cohorts**

| Cohort  | Drug a,b,c | Window   |   | Triplet Combination  |  |
|---------|-----------------------|--|---|--|--|
|         |                       | Cycle-2
Cohorts 3, 4, 5,
and 6: 28 days
a,b,c    | Cycle-1
Cohorts 3, 4, 5,
and 6: 28 days
a,b,c | Cycle 1
Cohort 3: 28 days
Cohort 4/5/6: 35 days
a,b,c                        | Cycles 2-12
Cohorts 3, 4, 5,
and 6: 28 days
a,b,c                      |
| 3       | Magrolimab            | D2: 1mg/kg
priming dose
D8,15,22:
30mg/kg | D1,15:
30mg/kg                                      | D1,15: 30mg/kg  | D1,15: 30mg/kg  |
|         | Obinutuzumab          | D1: 100mg
D2: 900mg
D8,15: 1000mg     | D1: 1000mg   | D1: 1000mg  | D1: 1000mg  |
|         | Venetoclax            | N/A  | N/A   | D1-28:
at target dose (dose
established from dose-
finding cohorts)          | D1-28:
at target dose
(dose established
from dose-
finding cohorts) |
| 4, 5, 6 | Magrolimab            | D2: 1mg/kg
priming dose
D8,15,22:
30mg/kg | D1,15:
30mg/kg                                      | D1,15: 30mg/kg  | D1,15: 30mg/kg  |
|         | Obinutuzumab          | D1: 100mg
D2: 900mg
D8,15: 1000mg     | D1: 1000mg   | D1: 1000mg  | D1: 1000mg  |
|         | Venetoclax            | N/A  | N/A   | D1-35:
ramp-up to target
dose (dose
determined from
dose-finding cohorts) | D1-28:
at target dose
(dose established
from dose-
finding cohorts) |

a When both magrolimab and obinutuzumab are given on the same visit day, obinutuzumab will be administered at least 1 hour after the completion of magrolimab administration.

b Premedication with acetaminophen 650 mg and diphenhydramine 25-50mg (or comparable regimen) will be administered 30-60 minutes prior to all obinutuzumab doses. Similar premedication will also be given prior to priming dose and first loading dose of magrolimab. Additional premedication with dexamethasone 4 to 20 mg, or comparable regimen will be given before the priming dose and first loading dose of magrolimab. Premedication is not required for subsequent doses of magrolimab.

c Obinutuzumab and magrolimab are administered as intravenous infusions.

### 3.2.1 Magrolimab Administration

All patients will receive a magrolimab priming dose of 1 mg/kg on Day 2 of the first cycle of treatment. The duration of infusion of the priming dose will be 3 hours ( $\pm 30$  minutes). Use of an inline filter is required. All subsequent loading or maintenance doses of magrolimab will be infused over a duration of 2 hours ( $\pm 10$  minutes). When both obinutuzumab and magrolimab are given on the same visit day, obinutuzumab will be administered at least 1 hour after the completion of

magrolimab administration. All patients should be monitored for 1 hour post-infusion for all doses during Cycle -2. Post-infusion monitoring should begin after the last study drug is given. Post-infusion monitoring is not required for doses after Cycle 1, Day 22 for Arms 1 and 2 (dose-finding arms), and Cycle -2, Day 22 for Arms 3 and 4 (dose expansion arms). Patients who experience any treatment-related AEs during the observation period should be further monitored, as clinically appropriate.

Complete Blood Count with Differential will be performed prior to each dose, and 3-6 hours after the first and second doses of magrolimab - Cycle 1, Days 2 and 8 for dose-finding arms (Arms 1 and 2), and Cycle -2, Days 2 and 8 for dose-escalation arms (Arms 3 and 4). Complete Blood Count with Differential will also be performed twice weekly for the first cycle (Cycle 1 for dose-finding arms [Arms 1 and 2], and Cycle -2 for dose-escalation arms [Arms 3 and 4]).

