**Table 8: Venetoclax dose-finding rules for Arms 1 and 2**

| Number of Patients with DLT at a Given Dose Level | Dose-Finding/Dose Decision Rules   |
|---|--|
| <2 out of 6                                       | This target dose will be used in expansion phase   |
| $\geq 2$ out of 6 at DL1                          | Six (6) patients will be entered at dose level (-1).   |
| $\geq 2$ out of 6 at DL (-1)                      | Further enrollment will be stopped, and a safety analysis will be performed to determine further course of action. |

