#### **3.4.2 Magrolimab**

##### **3.4.2.1 Anemia**

Treatment with a priming dose of 1 mg/kg followed by higher weekly maintenance dosing is associated with an early, transient, acute decline in hemoglobin levels of about 2 g/dL, with nadirs occurring in most patients within the first 2 weeks of starting therapy. In most patients with adequate bone marrow reserve, hemoglobin levels gradually recover to baseline by Week 4 or later, despite continued treatment with magrolimab. Based on these data, all patients must have a documented hemoglobin  $\geq$  9 g/dL within 24 hours prior to each of the first 2 doses of magrolimab infusion during initial treatment. Patients who do not meet these criteria must be transfused and have their hemoglobin rechecked to meet  $\geq$  9 g/dL prior to each of the first 2 doses of magrolimab. For patients after exposure to magrolimab, hemoglobin will be monitored frequently for response

and/or toxicity prior to each dose, and 3 to 6 hours after the initiation of the first and second doses of magrolimab. The patient should be transfused as clinically appropriate.

Magrolimab binds to RBCs and may cause transient interference with cross-matching of units for transfusion. During the screening period, red blood cell typing per NIH CC guidelines will be performed for each patient. For all elective red cell transfusions, leukocyte-reduced units matched for the phenotype of the patients will be used. Where exact matching for all the specified blood groups proves impractical (e.g., for MNS blood group), local sites will decide on the best matched donor units to be used. Cytomegalovirus (CMV) matching (i.e., CMV-seronegative units for CMV-seronegative patients) will not be required for this study because it will limit the inventory for antigen matching.

If the crossmatch is incompatible, the RBC units that are Coombs crossmatch-incompatible will be selected (e.g., phenotype-matched or least incompatible) for issue at the discretion of the local site's Transfusion Service Medical Director or equivalent person, where available. For emergency transfusions, the transfusion laboratory may consider using emergency Group O Rhesus negative units if phenotyped units are not available. Blood plasma therapy will be blood-type specific. Platelets will be blood type compatible whenever possible, and if not, will have been tested and found not to have high titer anti-A or anti-B.

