#### 3.4.2.4 Severe Neutropenia Prophylaxis

Severe neutropenia and febrile neutropenia were reported in patients treated with magrolimab in combination with chemotherapy. Close monitoring of hematologic parameters including neutrophils is required for all patients treated with magrolimab. For patients with high risk of developing Grade 4 neutropenia and febrile neutropenia, primary and secondary prophylaxis with G-CSF is highly recommended. Prophylactic use of antimicrobials may be considered at the discretion of the treating physician. Management of neutropenia and dose modifications will be per Section [3.3.2](#).

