### **3.5 ON STUDY EVALUATIONS**

Upon successful enrollment, and following completion of the Screening/Baseline visits, patients will begin treatment as outlined in Section [3.1](#). The results from all procedures/tests must be reviewed prior to initiation of each cycle of treatment for consideration of dose modifications.

Treatment with magrolimab, obinutuzumab, and venetoclax will continue until discontinuation per study protocol (Section [3.1](#)), disease progression, unacceptable treatment-related toxicity, or other reasons outlined in Section [3.9](#). Refer to the Study Calendar ([Appendix G](#)) for additional information for all tests and procedures to be performed prior to each visit and in follow-up.

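### In triplet Cycle 1 of Cohorts 4-6, no blood count is dated between D15 and C2D1, so the latest dated count is 7 days old at the 200 mg step and, at DL1, 14 days old at the 400 mg step

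*Combined protocol and SAP*

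**What the plan says.** Four parts of the protocol set the dated CBCs for Cohorts 4-6 in triplet Cycle 1.

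- **Section 3.2.1** requires a CBC before each dose, plus counts "twice weekly for the first cycle (Cycle 1 for dose-finding arms [Arms 1 and 2], and Cycle -2 for dose-escalation arms". For Arms 3 and 4 the twice-weekly period is thus Cycle -2, the first window cycle. Section 3.4.2.1 words the dose-linked rule for hemoglobin in the same way: "prior to each dose, and 3 to 6 hours after the initiation of the first and second doses of magrolimab".
- **Table 12** gives the cycle length as "Cohort 4/5/6: 35 days", with magrolimab on D1 and D15 and obinutuzumab on D1.
- **Appendix G** adds D1 of each cycle. Its footnote 7 repeats the dose-linked rule and names no other Cycle 1 day for these cohorts.
- **Table 10** applies the weekly ramp-up to Arm 4 as well as Arm 2.

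Other text bears on blood counts without dating any. Section 3.4.2.4 states: "Close monitoring of hematologic parameters including neutrophils is required for all patients treated with magrolimab". Section 12.3.1 sets a monthly minimum. Section 3.5 states: "The results from all procedures/tests must be reviewed prior to initiation of each cycle of treatment for consideration of dose modifications". Table 19 recommends pre-dose samples at the later ramp-up steps, but these are chemistry, which Section 4.1.2.1 lists as potassium, uric acid, phosphorus, calcium and creatinine.

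**The concern.** Section 3.1.5 sends ramp-up dose changes to Section 3.3.2. There, Table 16 holds venetoclax during triplet therapy for Grade 3-4 neutropenia (with or without fever), thrombocytopenia or anemia. Afebrile neutropenia in particular may give the patient no reason to call, so the hold works reliably only if a count is drawn.

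The two undated steps lead to the highest doses of the ramp-up, and Section 1.2.8.2 itself notes a trend to more neutropenia at higher venetoclax doses in combination. Table 9 lets venetoclax start at an ANC of 1,000, which is the upper edge of Grade 3 as Section 12.3.1 gives it. If a silent Grade 3-4 cytopenia began after D15 and no unscheduled CBC was drawn, the dose could be raised when the plan's own rule says to hold it.

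**Working it through.** The plan states no figure for the age of a count, so this is day arithmetic on its schedule.

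**Inputs.** Cycle 1 = 35 days (Table 12), so C2D1 = D36. Step day = 7 × (week − 1) + 1, with weekly doses from Table 10. Dated CBCs: D1 (calendar and pre-magrolimab) and D15 (pre-magrolimab). Obinutuzumab on D1 adds no further day.

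**Age of the latest dated count = step day − last CBC day.**

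| Step | Venetoclax | Last dated CBC | Age |
|---|---|---|---|
| D1 | 20 mg | D1 | 0 days |
| D8 | 50 mg | D1 | 7 days |
| D15 | 100 mg | D15 | 0 days |
| D22 | 200 mg | D15 | 22 − 15 = 7 days |
| D29 | 400 mg (DL1 only) | D15 | 29 − 15 = 14 days |

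The D15 count, taken before dosing, follows only the 20 mg and 50 mg weeks. At DL(-1) the dose stays at 200 mg in week 5, so D29 is not a step.

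**Length of the gap.** Nominal: 36 − 15 = 21 days. Section 3.2 adds: "A flexibility window between cycles of -3/+7 days is allowed due to scheduling or other administrative reasons". C2D1 can then fall from D33 to D43, giving 18 to 28 days. Appendix G also allows the D1 assessments up to 3 days early. If both windows apply, the earliest draw is D30 and the gap is 15 to 28 days. Even D30 comes after both steps.

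**Onset with a step still to come.** DL1: D15-D28, 14 of the 21 days. DL(-1): D15-D21, 7 of 21.

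**Onset after the last step.** No further increase is at stake, only a delayed hold: up to 36 − 29 = 7 nominal days at DL1, and up to 36 − 22 = 14 at DL(-1).

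**Reading of the dose-linked rule.** I take it to mean magrolimab doses, because it stands in the magrolimab section and continues with that drug's first and second doses. Applied to daily venetoclax it would require a CBC every day, which nothing else in the plan supports. Limited to the listed Cycle -2 days, it would leave C1D1 as the last count, with ages of 22 − 1 = 21 and 29 − 1 = 28 days.

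**With the fix.** DL1 (D1, 15, 22, 29, 36): gaps 14, 7, 7, 7 days. DL(-1) (D1, 15, 22, 36): gaps 14, 7, 14 days. Each step after D15 has a same-day count.

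**The case against.** The best defense is that the plan combines dated tests with clinical judgment. Table 9 requires an ANC of at least 1,000, platelets of at least 50,000 and hemoglobin of at least 9 g/dL before venetoclax is added. By then most patients have had two cycles of the doublet, the first with twice-weekly counts. Section 3.4.2.4 makes close neutrophil monitoring mandatory and strongly recommends growth-factor prophylaxis for high-risk patients. Appendix G allows any further test the investigator thinks indicated, and the monthly minimum is met. All of this stands, and it makes the point modest. It does not close the gap: the Table 9 check and the window come before any venetoclax, and the rest names no day.

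The D8 step also rests on a 7-day-old count. That is true. The distinctive feature is the 14-day-old count at D29, together with the size of the doses at D22 and D29.

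A reader might draw four stronger conclusions that the documents do not support.

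- *That each increase relies on an outdated count.* No text makes a step conditional on a CBC; Table 16 responds to toxicity once it is known.
- *That the contrast with Arm 2 shows a venetoclax safeguard was removed.* Arm 2 has twice-weekly counts over the same ramp-up, but Section 3.2.1 attaches them to the first cycle of treatment, when magrolimab is new. In Arm 2 that is also the DLT window.
- *That the expansion dose is in doubt.* Table 8 says of a dose that passes, "This target dose will be used in expansion phase", and that decision rests on Arms 1 and 2, whose counts are not affected.
- *That a known share of patients would be harmed.* Grade 3-4 neutropenia was 11% with venetoclax alone in 106 NHL patients (Section 1.2.5.1) and 112/212 = 53% with venetoclax-obinutuzumab in CLL (Table 6). Those rates cover other regimens and whole treatment courses, not three weeks of ramp-up.

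**Conclusion.** The point holds as a cheap safety improvement. The written schedule dates no CBC from after D15 until C2D1, a nominal 21 days, and both late dose increases (one at DL(-1)) fall in that gap. It concerns up to 6 MZL + 12 MCL + 6 CLL = 24 patients, for one cycle each.

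This rests on reading the dose-linked CBC rule as magrolimab doses, and it matters only where no unscheduled CBC is drawn. The plan gives no rate of cytopenia during ramp-up, so no expected number of missed holds can be stated. The DLT analysis and the choice of expansion dose are unaffected.

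**What to change.** In Section 3.2.1 and Appendix G footnote 7, require a CBC with differential on D22 and, at DL1, on D29 of triplet Cycle 1 in Cohorts 4-6. Draw it with the Table 19 pre-dose chemistry and review it before that day's venetoclax dose. D8 may be added in the same way. Name the days outright, because Section 4.1.2.1 lets the investigator modify the Table 19 schedule. Cohort 3 needs no change on this ground: FL patients start at target dose and have no later step.

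The cost is protocol wording and one extra tube at draws already recommended, or a separate draw where the investigator has dropped the chemistry. The downside is slightly more recorded cytopenias and venetoclax holds in these cohorts.

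The change does not shorten the wait for C2D1 after the last step: up to 7 nominal days after D29 at DL1, and up to 14 after D22 at DL(-1).

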### 3.2.1.1 Premedication for magrolimab

The optimal pretreatment regimen is defined as acetaminophen 650 mg (or a comparable non-steroidal anti-inflammatory agent) and oral or IV diphenhydramine 25 to 50 mg (or comparable regimen) for the priming dose and the first loading dose. Additional premedication with dexamethasone 4 to 20 mg will be given before the priming dose and first loading dose of magrolimab. Premedication is required before administration of the first 2 doses of magrolimab. Premedication is not required for subsequent doses unless the patient has experienced a prior grade 3 infusion reaction; however, premedication for subsequent magrolimab treatments may be continued based on the treating physician's clinical judgement and the presence/severity of prior infusion reactions. Intravenous corticosteroid (e.g., 100mg prednisone/prednisolone or 4 to 20mg dexamethasone or 80mg methylprednisolone) may be administered if a patient has experienced a prior grade 3 infusion reaction, or at investigator's discretion.

### 3.2.2 Obinutuzumab Administration

**Table 13: Dose and infusion rate of obinutuzumab for all patients**

| Day of treatment cycle                        | Dose of obinutuzumab | Rate of infusion   |
|---|----------------------|--|
| Cycle 1
(Dose-finding,
Arms 1 and 2)    | Day 1                | 100 mg
Administer at 25 mg/hr over 4 hours. Do not increase the infusion rate.  |
|   | Day 2                | 900 mg
If no IRR occurred during the previous infusion, administer at 50 mg/hr.
The rate of the infusion can be escalated in increments of 50 mg/hr every 30 minutes to a maximum rate of 400 mg/hr.
If the patient experienced an IRR during the previous infusion, start administration at 25 mg/hr. The rate of infusion can be escalated in increments of up to 50 mg/hr every 30 minutes to a maximum rate of 400 mg/hr. |
|   | Day 8                | 1000 mg
If no IRR occurred during the previous infusion where the final infusion rate was $\geq$ 100 mg/hr,   |
| Cycle -2
(Dose expansion,
Arms 3 and 4) | Day 15               |  |

| Day of treatment cycle              |       | Dose of obinutuzumab | Rate of infusion  |
|--|-------|-----------------------------|--|
| Cycle 1
(Dose-finding,
Arms 1 and 2) | Day 1 | 100 mg                      | Administer at 25 mg/hr over 4 hours. Do not increase the infusion rate.  |
|  | Day 2 | 900 mg                      | If no IRR occurred during the previous infusion, administer at 50 mg/hr. The rate of the infusion can be escalated in increments of 50 mg/hr every 30 minutes to a maximum rate of 400 mg/hr.  |
|  | Day 8 | <del>1000 mg</del>          | If the patient experienced an IRR during the previous infusion, start administration at 25 mg/hr. The rate of infusion can be escalated in increments of up to 50 mg/hr every 30 minutes to a maximum rate of 400 mg/hr.   |
| All subsequent cycles (all arms)           | Day 1 | 1000 mg                     | If no IRR occurred during the previous infusion infusions can be started at a rate of 100 mg/hr and increased by 100 mg/hr increments every 30 minutes to a maximum of 400 mg/hr. If the patient experienced an IRR during the previous infusion administer at 50 mg/hr. The rate of the infusion can be escalated in increments of 50mg/hr every 30 minutes to a maximum rate of 400 mg/hr. |

